3. STUDY HYPOTHESIS

isCGM combined with nurse certified diabetes educator (CDE) education and feedback will improve glycemic control and patient self-management of diabetes compared to enhanced usual care with CDE education and feedback only.

4. STUDY OBJECTIVES

Primary Objective

To evaluate the effectiveness of isCGM with CDE education and feedback on glycemic control at 12 weeks, in adults with type 2 diabetes and uncontrolled HbAc ($> 7.0\%$) not on insulin therapy.

Secondary Objectives

To determine the feasibility of recruiting adults with diabetes in Edmonton-area to a trial of glucose self-monitoring and education.

To determine the effectiveness of isCGM with CDE education and feedback on patient self-management of diabetes, measured using patient reported instruments for diabetes-related quality of life, diabetes treatment satisfaction, diabetes self-management empowerment, diet, and physical activity – at 6 weeks and at 12 weeks.

To determine the safety of isCGM with CDE education and feedback with respect to emergency department visits or hospitalizations, and isCGM-specific reactions (e.g.: skin reactions).

To understand the reasons *why* or *how* isCGM with CDE education is effective or ineffective from the perspective of involved participants and their providers.

To evaluate the effectiveness of isCGM with CDE education and feedback on glycemic control at 24-52 weeks (post-trial observational follow-up).

5. isCGM (INTERMITTENTLY SCANNED CONTINUOUS GLUCOSE MONITOR) – DESCRIPTION OF TECHNOLOGY

Technology – The only isCGM on the market at this time is the FreeStyle Libre 2 system produced by Abbott. FreeStyle Libre 2 sensors use a subcutaneous, wired enzyme glucose-

sensing technology, factory-calibrated to detect glucose levels in *interstitial* fluid by way of a thin filament implanted under the skin. The sensors are water-proof, affix to the skin by medical adhesive, last 14 days each, and are roughly the size of two stacked quarters. They measure interstitial glucose every minute, with readings stored in 15-minute intervals. Patients can scan sensors on-demand, using either a near-field communication-enabled smart phone or the FreeStyle Libre 2 Reader, to receive a glucose result along with historic results for the preceding 8 hours. The FreeStyle Libre 2 system is fully marketed in Canada; in 2020, it's predecessor, the similar FreeStyle Libre flash glucose monitoring system, had over 2 million users internationally.³²

Market Access / Licensing – The Libre 2 flash glucose monitoring system has been licensed by Health Canada since November 30, 2020 (No. 105518) for measuring interstitial fluid glucose levels in children aged 4 years and older and adults with diabetes mellitus.^{33,34}

Accuracy – Compared to reference venous blood glucose measurements, Libre 2 sensors had a mean absolute relative difference (mARD) of 9.2%, with over 78% of values within +/- 15% of reference values, and over 88% of values within +/- 20% of reference values, across the physiologic range of blood glucose.³⁵ These values are improved from the preceding Libre flash glucometer system, which demonstrated mARD 11.4% (overall 85% of values within +/- 20% of reference).³⁶ An error analysis of the preceding Libre flash glucometer system showed that the difference between Libre glucose readings and capillary blood glucose measurements would lead to a difference in treatment in < 1% of readings.³⁶ Based on these data, interstitial glucose values can be used interchangeably with capillary blood glucose measurements, though users should be aware that interstitial glucose may lag behind venous blood glucose by 2.4 +/- 4.6 minutes.³⁵

Reliability – Simultaneous tests of paired sensors yielded blood glucose results with a coefficient of variation of 5.7%, indicating good agreement between sensors.³⁵

Data presentation – Upon scanning the sensor, the current glucose result is displayed for the patient, along with arrows indicating current glucose trends (i.e.: rising quickly, rising, changing slowly, falling, falling quickly) based on the rate of glucose change. Historic results are displayed in the “daily graph” as a line plot, providing a visual reference for the day’s glucose peaks and valleys.

Remote patient telemonitoring – Internet-enabled smart phones can be configured to automatically push glucose data to LibreView, an online portal for patients and providers to review glucose data. Similar functionality using the Libre 2 Reader requires users periodically to connect their reader to a computer via USB. Providers can set up a LibreView account for their clinics, allowing access to glucose reports for multiple enrolled patients. LibreView provides sophisticated glucose reports, including glucose statistics and ambulatory glucose profiles (median and inter-quartile range), in addition to daily glucose profiles.

6. STUDY DESIGN

This trial is an investigator-initiated prospective, single-center, open-label, randomized controlled trial of isCGM with CDE education and feedback. All participants will receive standard treatment at the discretion of their physicians.

Setting

- Tertiary care ambulatory referral clinic in Alberta, Canada, with recruitment of patients from urban primary care practices.

Intervention – isCGM + CDE Education and Feedback

- *Short Term Use of isCGM* – Participants will be given three FreeStyle Libre 2 sensors during the study period. Each sensor, once worn, provides glucose measurements for 14 days. The three sensors will provide 6 weeks of isCGM. Participants will *not* be encouraged to use FreeStyle Libre 2 sensors outside of the intended study periods, but neither will they be discouraged from doing so if they choose to of their own accord. The first sensor will be initiated with the assistance of a study team member, who will also set up the Libre 2 smart phone app and link it to the study LibreView account during the baseline visit. Subsequent sensors will be participant-initiated. Should participants encounter difficulty with sensor placement, replacement sensors will be made available, and participants will be referred to their local retail pharmacist to assist with sensor initiation. A small number of FreeStyle Libre 2 Readers will be available for those with unforeseen technical difficulties. Patients using the readers will be asked to upload their data to LibreView online via USB adapter connection to their computers, on a weekly basis.
- *Initial Patient isCGM Training* – Participants will be provided multimedia materials (written booklet and link to bespoke introductory videos) to help them understand and trouble shoot the Libre 2 system, and to help them understand their glucose readings and act on them. These materials will be designed with patient and CDE-input using a human-centred design process via the University of Alberta’s Physician Learning Program (in process), and may also include multimedia resources produced by Abbott, the manufacturer of the Libre 2 isCGM. Additionally, participants will be referred to Alberta Health Service’s standard diabetes education group classes and advised to register according to their interest and motivation. Diabetes Canada and Alberta Health Services-concordant advice and handouts will be provided to isCGM participants on recognizing and managing hypoglycemia (<https://www.albertahealthservices.ca/assets/mha/diabetes/mha-diabetes-hypoglycemia-the-basics.pdf>).
- *CDE Education and Feedback* – A CDE nurse will assess the participant and review her/his LibreView data. The CDE nurse will provide general diabetes education and advice on using isCGM, and individualized recommendations on lifestyle (diet and physical activity) changes to improve glycemic control. Two encounters will take place with the CDE nurse. The first will occur during weeks 1-2, and the second during weeks 5-6,. During the second encounter, CDE nurses may also consider sending recommendations to participants’ usual care providers for medication titration, if appropriate. CDE nurses will provide education and advice according to their usual training and practices. General guidance on incorporating isCGM readings into

individualized advice for participants and their care providers will be provided in the form of a clinical algorithm, which will also be designed with patient and CDE-input using a human centred design process via the University of Alberta's Physician Learning Program (in process). CDE encounters will take place either in-person, or virtually, over Zoom.

Control – Enhanced Usual Care With CDE Education and Feedback Only

- *No specific monitoring of glucose* – Participants will be discouraged from accessing FreeStyle Libre 2 glucometers or other CGM during the study period. They will be free to use capillary blood glucose monitoring according to their own interest and motivation, or as directed by the CDE nurse. Advice and handouts will be provided to isCGM participants on recognizing and managing hypoglycemia.
- *Alberta Health Services Diabetes Education Group Classes* – Participants will be referred to Alberta Health Service's standard diabetes education group classes and advised to register according to their interest and motivation.
- *CDE Education and Feedback* – A CDE nurse will assess the participant. The CDE nurse will provide general diabetes education, and individualized recommendations on lifestyle (diet and physical activity) changes to improve glycemic control. Two encounters will take place with the CDE nurse. The first will occur during weeks 1-2, and the second during weeks 5-6. CDE nurses will provide education and advice according to their usual training and practices. CDE encounters will take place either in-person, or virtually, over Zoom.

Study period – The trial period will be 12 weeks. From 12 weeks onwards, select participants will be approached to participate in semi-structured qualitative interviews. Linkage of participant information to Alberta administrative health care data may occur up to 3 years after trial completion to allow examination of diabetes outcomes on an observational basis up to 52 weeks from randomization.

Blinding

- This trial is open-label. Neither patients, investigators, nor statistical analysts will be blinded to treatment allocation.

Post-Trial Observational Follow-Up – Patients will be reviewed on NetCare for laboratory values and health care utilization at 24 and 52 weeks following randomization. NetCare data accrued up to 64 weeks post-randomization will be reviewed to identify nearest lab values for the 52-week time point.

Post-Trial Qualitative Study of Experiences Using isCGM – Consenting patients and providers will be contacted after the 12 week study period to participate in semi-structured interviews exploring their experiences using isCGM or managing their blood glucose without isCGM.

7. STUDY POPULATION

Adults (age ≥ 18 years) with type 2 diabetes and uncontrolled blood sugars, defined as HbA1c $> 7.0\%$, not on insulin therapy.

Inclusion Criteria:

1. Age ≥ 18 years with type 2 diabetes.
2. HbA1c $> 7.0\%$ within the last 6 months.
3. Non-insulin therapy.
4. Able to attend two in-person study visits.
5. English-speaking.
6. Community-dwelling
7. In possession of a cell phone capable of accessing the internet and receiving FreeStyle Libre 2 sensor readings
8. Has a primary care provider who has been in contact with the patient for diabetes in the last 12 months.

Exclusion Criteria:

1. Type 1 diabetes or diabetes clearly identified as having monogenetic etiology (e.g.: MODY).
2. Steroid-induced diabetes if steroid use is on-going or most recently taken within the last 3 months.
3. Pregnancy; plans to become pregnant within 6 months; breast-feeding.
4. Any use of insulin in the previous year.
5. Current or previous use of isCGM or rtCGM.
6. Cognitive dysfunction (SPMSQ score ≥ 5).
7. Symptoms of acute metabolic decompensation (extreme thirst, high urinary output, and weight loss, accompanied by acute fatigue or dyspnea).
8. Any terminal condition that would limit life expectancy to < 1 year.
9. Inability to use isCGM (e.g.: afraid of the device).
10. Inability to be reached by telephone.
11. Concurrent participation in another diabetes-related trial.
12. Has not already received two doses of a Health Canada-approved vaccine against SARS-CoV-2.

8. RECRUITMENT STRATEGIES

A multifaceted recruitment strategy will be deployed to identify patients meeting study criteria from the following sources:

1. Kaye Edmonton Clinic (KEC) General Internal Medicine (3D), Endocrinology (3B), and Family Medicine (1A) clinics.
2. Regional Diabetes Program (RDP) clinics
3. C-ENDO, a multi-site privately administered endocrinology and internal medicine clinic in Edmonton

4. Primary Care Networks (PCN) and family medicine clinics, including Covenant Health sites.
5. Participant self-referral

For sources (1) through (4), above, outreach efforts will involve

- Identification of site “champions” to promote with recruitment – most likely to involve non-physician personnel (diabetes educators, dieticians).
- Presentations to clinic providers (physicians, diabetes educators, and dieticians) at staff/business meetings or divisional meetings.
- Dear Provider Letters – Appendix 1.
- Brochures featuring large graphics placed in exam and waiting rooms (with permission) – Appendix 2.
- Social media advertising via Facebook, Twitter, and study landing page, and through recruitment networks such as Bethecure.ca

We will ask providers – both physicians and non-physicians – to refer interested patients to study investigators for the study team to contact and screen. In our recruitment materials, we emphasize the potential benefit to participants being access to FreeStyle Libre 2 sensors on a trial basis with linkage to personalized CDE advice; regardless of randomization group, participants will be remunerated for the time and inconvenience of study participation (including labwork) with a honoraria consisting of gift cards (Walmart or Safeway or similar grocery store) of \$40 CAD upon receipt of baseline and 12-week follow-up HbA1c measurements, and will have their parking fees paid. Study investigators will not enroll their own patients.

9. PARTICIPANT CONSENT

Following a screening phone call, eligible patients will attend a baseline visit to complete consent for participation and randomization, as well as completion of baseline measures. For the initial screening, verbal consent (Appendix 3.1) will be obtained from potential study participants to access their provincial NetCare electronic medical records and confirm that they meet the HbA1c inclusion criteria.

A study investigator or research assistant will review the nature of the clinical trial, and the anticipated risks and benefits. An electronic trial information sheet and consent form will be created by EpiCore Centre (Appendix 3.2). The trial consent form will be signed by the patient either using a touch-interface (e.g.: iPad or similar device) or using a mouse to draw a signature (desktop computer), and witnessed by the study investigator or research assistant. The patient’s email address will be collected, and once the consent is signed, a copy will be emailed to the participant. In the event of technical difficulties, a participant without email access, or a participant that refuses electronic signing, paper copies of both the trial information sheet and consent forms will be available. An additional paper copies of the consent form, in that case, will be signed and given to the participant to take home.

Select providers (referring physicians / educators / dieticians and the study CDE nurse) will be approached and consented for semi-structured interviews to contribute their perspective on the use of isCGM. A specific information package and consent form for the qualitative sub-study (providers only – patients are covered by the full trial consent package) has been developed (Appendix 3.3).

Patients will be free to withdraw consent / withdraw from the study at any time, and will be given written instructions on termination of Libre 2 data sharing as part of the study information package (Appendix 4).

10. STUDY OUTCOMES AND VARIABLES

Case report forms are provided in Appendix 5. These will be translated into electronic documents to be completed by participants via a password protected webportal (EpiCore).

Primary Outcome:

- Change in HbA1c at 12 weeks compared to baseline.

Secondary Outcomes:

- Feasibility of recruitment
 - Participant referral, screening, and randomization rates over time
 - Reasons for inclusion / exclusion of all participants referred.
- Change in scores at 6 and 12 weeks compared to baseline, on the patient-reported outcomes shown in Table 1, below.
- isCGM participants only – change in time-in-target range, coefficient of variation, and glucose management indicator at 12 weeks compared to baseline.

Table 1: Patient-Reported Outcomes

Outcome	Instrument	Number of items
Diabetes treatment satisfaction – Status score	Diabetes Treatment Satisfaction Questionnaire (DTSQs) ³⁷ (weeks 6 and 12)	8
Diabetes treatment satisfaction – Change score	Diabetes Treatment Satisfaction Questionnaire (DTSQc) (week 6 only)	
Self-management empowerment	Diabetes Empowerment Scale – Short Form (DES-SF) ³⁸ (weeks 6 and 12)	8
Diabetes-related distress	Problem Areas in Diabetes (PAID) Questionnaire ³⁹	20
Diet	UK Diabetes and Diet Questionnaire (UKDDQ) ⁴⁰ (weeks 6 and 12)	25
Physical activity	International Physical Activity Questionnaire (IPAQ) short form ^{41,42} (weeks 6 and 12)	7
Health status	Euroqol EQ-5D-5L (weeks 6 and 12)	5

* In addition to collection at baseline.

Safety outcomes at 12 weeks:

- Any adverse events (serious and non-serious) occurring from baseline to 12 weeks will be identified and tracked at the 12 week study visit by patient interview, and reviewed

by study investigators to determine whether clinically attributable to diabetes, diabetes management, or isCGM. isCGM issues (e.g.: skin reactions) will be specifically sought.

- Emergency department visits or hospital admission for any reason, identified from patient interview and from NetCare review.

Qualitative Outcomes: Semi-structured interviews will undergo thematic analysis using constant comparative methods. The starting point will be the participant and provider experience with isCGM or enhanced usual care, with a particular focus on barriers and enablers of effectiveness (see Appendix 6, interview guides). Semi-structured interviews will take place for participants after trial completion (from 12-24 weeks).

24-52 Week Post-Trial Observational Follow-up: After the trial ends, we will send out reminder letter to all participants and their providers encouraging them to have routine diabetes assessments, including laboratory measures, done. We will ascertain the effect of the intervention on HbA1c at 24 and 52 weeks, by review of NetCare. NetCare data up to 64 weeks post-randomization may be reviewed to assign the nearest lab value to the 52 week time point.

Other Quantitative Variables Measured:

Case report forms are provided in Appendix 5.

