13. TREATMENT-EMERGENT ADVERSE EVENTS

Included participants belong to a population (adults with type 2 diabetes and are not on insulin) that does not typically experience hypoglycemia, and do not typically measure their glucose levels. No serious adverse events are expected. However, this protocol has several features to identify unexpected adverse events during the study.

- All emergency department visits and hospitalizations occurring from randomization to week 12 will be reviewed and adjudicated (see Appendix 5.6 for adverse event reporting forms) by study investigators. If a serious adverse event occurred because of the trial or trial intervention, study protocols will be reviewed and amended to mitigate the harm.
- We are performing in-person visits with participants to measure BP and weight. There is the possibility that we detect extremely abnormal physical parameters (e.g.: severe hypertension $\geq 180/110$ mmHg, severe hypotension SBP < 90 mmHg). A study investigator will be paged if a result this extreme is detected and the participant will be advised to attend the emergency department.
- For emotional or psychological distress disclosed during a study visit or interview, the interviewer will offer supportive listening, remind participants of their right to withdraw from the trial, offer to connect the participant with a study investigator, and refer participants back to their usual care provider.

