Appendix 5.4: Patient-reported outcomes forms

isCGM Use

Follow-up time: 6 weeks, 12 weeks

In the last 6 weeks, have you used a continuous glucose monitoring sensor?
If yes, please indicate how many?

In the last 6 weeks, have you measured your blood sugars by finger prick?

Diabetes Treatment Satisfaction Questionnaire Status (DTSQs)

Follow-up time: Baseline, 6 weeks, 12 weeks

Date completed

Customized prompt: The following questions are concerned with the treatment for your diabetes (including blood glucose measurement, if applicable, and tablets and/or diet) and your experience over the past few weeks. Please answer each question by circling a number on each of the scales.

Diabetes Treatment Satisfaction Questionnaire: DTSQs

The following questions are concerned with the treatment for your diabetes (including insulin, tablets and/or diet) and your experience over the past few weeks. Please answer each question by circling a number on each of the scales.

1. How satisfied are you with your current treatment?
 very satisfied 6 5 4 3 2 1 0 very dissatisfied

2. How often have you felt that your blood sugars have been unacceptably high recently?
 most of the time 6 5 4 3 2 1 0 none of the time

3. How often have you felt that your blood sugars have been unacceptably low recently?
 most of the time 6 5 4 3 2 1 0 none of the time

4. How convenient have you found your treatment to be recently?
 very convenient 6 5 4 3 2 1 0 very inconvenient

5. How flexible have you found your treatment to be recently?
 very flexible 6 5 4 3 2 1 0 very inflexible

6. How satisfied are you with your understanding of your diabetes?
 very satisfied 6 5 4 3 2 1 0 very dissatisfied

7. Would you recommend this form of treatment to someone else with your kind of diabetes?
 Yes, I would definitely recommend the treatment 6 5 4 3 2 1 0 No, I would definitely not recommend the treatment

8. How satisfied would you be to continue with your present form of treatment?
 very satisfied 6 5 4 3 2 1 0 very dissatisfied

Please make sure that you have circled one number on each of the scales.

NOT FOR USE: For information only. [name]. HPR4704
 DTSQs © [name] 9/93 English for Canada 20.1.06 (from Standard UK English rev. 7/94)
 Health Psychology Research, UK. www.healthpsychologyresearch.com

Diabetes Treatment Satisfaction Questionnaire Change (DTSQc)

Follow-up time: 6 weeks only, following DTSQs

Date completed

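### Sensor skin reactions and other community-managed adverse events are sought only once, at week 12, about 4–6 weeks after planned sensor wear ends, although a week-6 questionnaire is already scheduled

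*Combined protocol and SAP*

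**What the plan says.** Section 10 (safety outcomes) sets the period, "Any adverse events (serious and non-serious) occurring from baseline to 12 weeks", and the method: events "will be identified and tracked at the 12 week study visit by patient interview". Device problems such as skin reactions are to be asked about specifically. Emergency visits and admissions have a second source; they are "identified from patient interview and from NetCare review". Section 13 has the investigators adjudicate all of them up to week 12, and Appendix 5.6 asks for the chart or discharge summary.

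The only form that prompts for adverse events and for skin reactions (type, treatment, whether use could continue) is the follow-up visit form, Appendix 5.3.

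On exposure, Section 6 says "Participants will be given three FreeStyle Libre 2 sensors during the study period", "Each sensor, once worn, provides glucose measurements for 14 days" and "The three sensors will provide 6 weeks of isCGM". The synopsis gives 6–8 weeks for the intervention. Both places leave participants free to obtain further sensors themselves.

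Section 10 schedules patient-reported outcomes at weeks 6 and 12 in both arms. The sensor-use form in Appendix 5.4, given at both times, asks "In the last 6 weeks, have you used a continuous glucose monitoring sensor", then the number of sensors and whether finger pricks were used. It asks nothing about harm. The educator encounters in weeks 1–2 and 5–6 (Section 6) carry no stated adverse-event enquiry.

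Section 4 makes reactions specific to isCGM part of a safety objective, and Section 11 treats skin reaction as the anticipated device risk.

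**The concern.** A mild or moderate skin reaction is an event that people forget or stop thinking worth mentioning once it has healed. The plan asks about it weeks after the last supplied sensor is due to come off, and asks once. For sensor use the same plan relies on a six-week recall window; for sensor harm it relies on twelve.

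Such reactions arise only in people wearing sensors, so forgotten ones would mainly lower the count in the isCGM arm and make the device look better tolerated than it was. A participant who misses the week-12 visit supplies no skin-reaction data at all under the plan. The retention efforts in Section 14 name HbA1c and the patient-reported outcomes, and none of those questionnaires contains a harm item. What is at stake is the device-safety result. The primary outcome is not touched.

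**Working it through.** **Inputs.** Three sensors of 14 days each (Section 6); intervention 6–8 weeks (synopsis); single interview at week 12 (Section 10); questionnaire at weeks 6 and 12 (Section 10, Appendix 5.4); target 100 participants (Section 14), allocated 1:1 (synopsis); expected loss 20–30% (synopsis).

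**Step 1: the plan's own figure.** 3 × 14 = 42 days = 6 weeks. The stated six weeks of isCGM is reproduced.

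**Step 2: gap from end of planned wear to the interview.**
- Six weeks of wear: 84 − 42 = 42 days, or 6 weeks.
- Upper synopsis figure of eight weeks: 84 − 56 = 28 days, or 4 weeks.

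**Step 3: recall lag now and with a week-6 enquiry.** Lag = week of enquiry − week of wear. The table assumes that the sensors are worn back to back from baseline.

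| Sensor | Weeks worn | Lag to week 12 | Lag to week 6 |
|---|---|---|---|
| 1 | 0–2 | 10–12 weeks | 4–6 weeks |
| 2 | 2–4 | 8–10 weeks | 2–4 weeks |
| 3 | 4–6 | 6–8 weeks | 0–2 weeks |

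The mean lag, from the midpoint of wear at week 3, is 12 − 3 = 9 weeks now and 6 − 3 = 3 weeks with the added enquiry. If wear is spread over eight weeks, the present lag is 4–12 weeks, with mean 12 − 4 = 8. In that case wear in weeks 6–8 would still be first asked about at week 12, at a lag of 12 − 8 = 4 to 12 − 6 = 6 weeks. On either figure, two enquiries six weeks apart leave no lag longer than about 6 weeks.

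**Step 4: participants with no interview.** 100 / 2 = 50 per arm. 50 × 0.20 = 10 and 50 × 0.30 = 15. This is an upper figure. It assumes that the expected loss applies equally to both arms and to the week-12 visit.

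**Step 5: what cannot be computed.** The documents give neither a skin-reaction rate nor a recall accuracy. Purely as an assumption, take a true rate of 5–20% in 50 wearers and recall of 60–100%. Expected recorded cases = 50 × (1 − loss) × rate × recall.
- Rate 5% (2.5 true cases): from 50 × 0.70 × 0.05 × 0.6 = 1.05 to 50 × 0.80 × 0.05 × 1 = 2.0.
- Rate 20% (10 true cases): from 50 × 0.70 × 0.20 × 0.6 = 4.2 to 50 × 0.80 × 0.20 × 1 = 8.0.

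These ranges show how the count depends on loss and recall. They are not estimates for this trial.

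**The case against.** The plan is stronger than a quick reading suggests. A reader might infer that serious events also rest on memory alone. The documents do not support that: emergency visits and admissions come from NetCare as well as interview and are adjudicated with their records. Section 10 fixes only the interview date and does not say when NetCare is reviewed, so one cannot conclude that such events stay unseen until exposure is over.

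A reader might also infer that the promise in Section 13, that "study protocols will be reviewed and amended to mitigate the harm", is empty because participants are past wear by week 12. The text does not promise protection to someone already exposed, and an amendment can still serve later enrollees. A questionnaire at day 42 would in any case arrive as back-to-back wear of the supplied sensors ends, so it would not answer that complaint.

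Further, Section 11 provides for referral and for barrier products before later sensors, which presupposes that some reactions surface during wear, and the educator sees participants twice in that time. This stands in part: spontaneous reports are likely to reach someone. But no enquiry or recording step before week 12 is described, so whether they enter the data is left open.

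Replacement and self-funded sensors can extend wear beyond week 6, so the gap is not a fixed six weeks. That is correct and is why the range is given. Finally, the week-12 interview does seek skin reactions directly, the device is licensed, the study is rated low risk, and safety results are declared hypothesis-generating. These points limit the weight of the concern but do not remove it.

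**Conclusion.** The point holds for adverse events that do not reach an emergency department or hospital, sensor skin reactions above all. They have one scheduled enquiry, 4–6 weeks after planned wear ends, with recall of about 4–12 weeks for the supplied sensors. Up to 10–15 of 50 isCGM participants could have no planned source of skin-reaction data.

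The consequence is a risk of under-counting that would flatter the device. A claim that reactions will certainly be under-counted goes further than the documents allow, since they give no rate and no recall accuracy. The lag figures rest on wear starting at baseline and finishing within the 6–8 weeks given; the loss figure rests on the assumptions in the working. This is a cheap improvement to safety ascertainment and does not bear on the primary analysis.

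**What to change.** Add to the week-6 questionnaire, in both arms, the adverse-event question and the skin-reaction items that already exist in Appendix 5.3. Route positive answers through the existing adverse-event form (Appendix 5.6) and investigator review. Keep the week-12 interview, and state in Section 14 that an event reported at either time counts once. Amend Section 10 to name both enquiries, and reconcile the six weeks in Section 6 with the 6–8 weeks in the synopsis so that the exposure period is clear.

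Participants lost between weeks 6 and 12 would then contribute device-reaction data; those lost before week 6 still would not. No visit, sample-size or primary-analysis change is needed. The cost is a few more items for participants and a real duty on the study team: the questionnaire may be completed at home through the portal, so someone must be assigned to look at positive week-6 answers promptly.
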